10.5 Final Analysis Plan

10.5.1 General Considerations

The SAP, which includes more technical and detailed elaboration of the principal features stated in the protocol, will be prepared separately and finalized before the interim analysis.

Safety will be assessed by estimating the occurrence of Grade 2 or higher treatment-emergent AEs in the IV bacteriophage therapies compared to placebo through Day 30 ± 7 days.

Microbiological activity will be assessed by estimating changes in $\log_{10} P. aeruginosa$ CFU/mL (total and each morphology) in sputum cultures from baseline through Day 30 ± 7 days.

The benefit to risk profile will be assessed by comparing the DOOR of IV bacteriophage arms and placebo arm through Day $8 + 3$ days. The DOOR will be analyzed by estimating the DOOR probability (Section 10.5.5), (i.e., the probability of a randomly selected subject having a better DOOR if assigned to receive an IV bacteriophage therapy compared to placebo).

All statistical calculations will be performed using up-to-date versions of SAS version 9.4 or higher (SAS Institute Inc., Cary, NC, USA) or language and environment for statistical computing 3.6.1 or higher (R Foundation for Statistical Computing, Vienna, Austria), unless otherwise specified. All PK analyses will be performed using NONMEM version 7.3 or higher (ICON Development Solutions, [name]). For continuous variables, summary statistics will include sample size, mean, SD, median, quartiles, minimum, and maximum values. Frequencies and percentages will be calculated for categorical variables. All reported confidence intervals will be two-sided 95%. Graphical displays will be produced.

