10.5.5 Analysis of Primary Endpoints

Grade 2 or higher treatment-emergent AEs will be summarized descriptively. The type of AE, number of events (n) and number (%) of subjects with events in each arm will be tabulated. The type of AE, number of AEs and the number (%) of subjects with events will be presented by system organ class (SOC), HLT, and preferred term. Subjects are counted once in each SOC, HLT, and preferred term. The difference in proportion of the number (%) of subjects with events between IV bacteriophage and placebo arms will be calculated with the corresponding exact 95% confidence interval.

Changes in \log_{10} *P. aeruginosa* CFU/mL (total and each morphology) in quantitative sputum cultures from administration of IV bacteriophages through Day 30 (\pm 7 days), Visit 7, will be summarized descriptively. Descriptive statistics will be presented by arms. The difference in mean change between IV bacteriophage and placebo arms will be estimated with the corresponding 95% confidence interval (\log_{10} -transformed and original scales). Area Under Curve (AUC) calculated using the trapezoidal rule will be used to summarize \log_{10} *P. aeruginosa* CFU/mL over the time. The difference in AUC between IV bacteriophage and placebo arms will be calculated with the corresponding 95% confidence interval.

The DOOR will be summarized by estimating the DOOR probability, using the equation

$$\text{DOOR probability} = \Pr[\text{DOOR}_{\text{IV}} > \text{DOOR}_{\text{P}}] + \frac{1}{2} \Pr[\text{DOOR}_{\text{IV}} = \text{DOOR}_{\text{P}}],$$

where DOOR_{IV} and DOOR_{P} are the DOOR for bacteriophage and placebo arms, respectively, and $\Pr[\text{DOOR}_{\text{IV}} > \text{DOOR}_{\text{P}}]$ is the proportion of a DOOR from IV bacteriophage dose exceeding a DOOR from placebo and $\Pr[\text{DOOR}_{\text{IV}} = \text{DOOR}_{\text{P}}]$ is the proportion of two DOOR outcomes being same. The corresponding 95% confidence interval will be calculated.

In addition, the DOOR will be analyzed as follows: DOOR distribution by arms, cumulative difference (point estimate and confidence band) in DOOR categories for bacteriophage vs. placebo, point estimate and confidence interval of difference in mean partial credit vs. placebo, and DOOR distribution for bacteriophage vs. placebo arm.

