### 8.1. Primary Analysis

#### 8.1.1. Safety Analysis

An event that occurs during the treatment period will be considered a TEAE if it was not present before the first dose of the study product or was present before the first dose of the study product and increased in severity during the treatment period.

The number of Grade 2 or higher TEAEs will be presented by Medical Dictionary for Regulatory Activities (MedDRA®) System Organ Class (SOC), High Level Term (HLT), and Preferred Term (PT) by treatment group in [Table 44](#). Subjects will only be counted once for each SOC and PT. The difference in proportion of the number of subjects with events between the Selected dose IV bacteriophage and placebo arms with the corresponding exact 95% CI will be presented in [Table 45](#). This is a primary endpoint and will be analyzed using the ITT population.

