[Implementation Note: If there is only 1 PT for an SOC, there will be no “Any PT” row.

Treatment group order: All subjects,  $4 \times 10^7$  PFU Dose,  $4 \times 10^8$  PFU Dose,  $4 \times 10^9$  PFU Dose, Placebo]

Treatment Group	MedDRA System Organ Class	MedDRA High Level Term	MedDRA Preferred Term	N	n (%)	95% CI a	Number of Events
All Subjects (N=X)	Any SOC	Any HLT	Any PT	x	x (x)	xx, xx	x
	[SOC 1]	Any HLT	Any PT	x	x (x)	xx, xx	x
		[HLT 1]	Any PT	x	x (x)	xx, xx	x
			[PT 1]	x	x (x)	xx, xx	x
	[SOC 2]	Any HLT	Any PT	x	x (x)	xx, xx	x
		[HLT 1]	Any PT	x	x (x)	xx, xx	x
			[PT 1]	x	x (x)	xx, xx	x
$4 \times 10^7$ PFU Dose (N=X)	...		...	x	x (x)	xx, xx	x
	...		...	x	x (x)	xx, xx	x
Placebo (N=X)	...		...	x	x (x)	xx, xx	x

Notes: N=Number of subjects in the ITT population in the specified Treatment Group.

n=Number of subjects with Grade 2 or higher treatment-emergent AEs.

A subject is only counted once per PT per treatment group and study part.

aExact Clopper-Pearson Confidence Interval.

**Table 45: Difference in Proportion of Grade 2 or Higher Treatment Emergent AEs in IV Bacteriophage vs. Placebo – ITT Population**

[Implementation Note: If there is only 1 PT for an SOC, there will be no “Any PT” row. This table will compare the Selected Dose of IV Bacteriophage to Placebo.]

MedDRA System Organ Class	MedDRA High Level Term	MedDRA Preferred Term	IV Bacteriophage n(%)	Placebo n(%)	Difference in Proportion	95% CI a
Any SOC	Any HLT	Any PT	x (x)	x (x)	x	xx, xx
[SOC 1]	Any HLT	Any PT	x (x)	x (x)	x	xx, xx
	[HLT 1]	Any PT	x (x)	x (x)	x	xx, xx
		[PT 1]	x (x)	x (x)	x	xx, xx
[SOC 2]	Any HLT	Any PT	x (x)	x (x)	x	xx, xx
	[HLT 1]	Any PT	x (x)	x (x)	x	xx, xx
		[PT 1]	x (x)	x (x)	x	xx, xx
...		...	x (x)	x (x)	x	xx, xx
...		...	x (x)	x (x)	x	xx, xx
...		...	x (x)	x (x)	x	xx, xx

Notes: n=Number of subjects with Grade 2 or higher treatment-emergent AEs.

A subject is only counted once per PT per treatment group and study part.

a95% CI for the difference in proportions, IV bacteriophage relative to placebo, calculated using the Miettinen–Nurminen method.

**14.3.1.2 Unsolicited Adverse Events****Table 46: Summary of Unsolicited Adverse Events by MedDRA System Organ Class, High Level Term, Preferred Term, and Treatment Group, Stage 1 – Safety Population**

[Implementation Note: If there is only 1 PT for an SOC, there will be no “Any PT” row.

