## 1. INTRODUCTION

After an interim analysis the optimal dose for Stage 2b was selected on 02FEB2024. The decision was unanimous among Phage Advisory Group (PAG) members and was made based on the benefit to risk profile that considered both the safety profile of bacteriophage preparations as well as the observed reductions in *P. aeruginosa* colony forming units (CFU)/mL. During review of the interim data the issue of several subjects having undetectable *P. aeruginosa* colony counts came to light, where the lower detection limit was  $10^4$  CFU/mL per colony morphology for Stage 2a. Due to the data collection practices prior to the interim analysis, if *P. aeruginosa* was not recovered in a sputum sample with MALDI TOF confirmation of genus/species then null results were entered for the colony counts. As there was no detectable result (i.e. missing in the dataset) entered for the colony counts for these samples, they were treated as missing during data analysis.

This detection limit issue was unexpected at the time of planning, and the statistical analysis plan (SAP, version 1.0, dated 14NOV2023) does not address how to handle data censored due to the limit of detection. Under this scenario the exact value of an observation is unknown but is known to be below the lower limit of detection. Of the 32 subjects in the interim analysis, 3 had undetectable *P. aeruginosa* colony counts at baseline and 2 had undetectable *P. aeruginosa* colony counts at every time point post-baseline. As they were treated as missing for the interim analysis, a change from baseline was not calculable for these 5 subjects and they did not contribute information to the two primary analyses, i.e., change from baseline and the Desirability of Outcome Ranking (DOOR). These subjects were still analyzed for safety outcomes that factored into the dose selection decision.

This document describes the planned analyses as related to undetectable results. Because an undetectable result may or may not be a valid result (i.e. the sample did not contain sputum), both an analysis employing imputation and a sensitivity analysis will be considered where undetectable is treated as missing to both match the assumption that was used during the interim analysis and to explore the robustness of the assumption that all undetectable results are valid.

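### In the final tables only the selected dose gets an estimated difference from placebo on the primary safety endpoint, which is narrower than the protocol's comparison and leaves the highest dose described by arm only

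*SAP*

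**What the plan says.** SAP 8.1.1 plans one between-arm estimate for subjects with Grade 2 or higher treatment-emergent AEs, taken "between the Selected dose IV bacteriophage and placebo arms". The note to the Table 45 shell repeats this: "This table will compare the Selected Dose of IV Bacteriophage to Placebo". Table 44 covers every dose and placebo with counts, percentages, number of events and a one-arm interval, footnoted "Exact Clopper-Pearson Confidence Interval". It has no difference column.

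Other parts of the plan are wider:

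- Protocol 10.5.1: "Safety will be assessed by estimating the occurrence of Grade 2 or higher treatment-emergent AEs in the IV bacteriophage therapies compared to placebo".
- Protocol 10.5.5 takes the difference "between IV bacteriophage and placebo arms will be calculated with the corresponding exact 95% confidence interval" and mentions no selected dose.
- SAP 6.1 groups safety tables and figures by the three doses and placebo. It reserves the two-group layout for microbiological activity and benefit-risk.
- The footnote to the SAP CONSORT figures restricts the ITT set to the optimal dose and placebo for the microbiological and DOOR endpoints only.

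On the dose choice, the introduction to the SAP addendum cites a benefit-risk profile that "considered both the safety profile of bacteriophage preparations as well as the observed reductions" in colony counts. The title of addendum Figure 23 shows that 4×10^8 PFU went into Stage 2b. Table 45 is not limited to Stage 2b, so the selected arm keeps its Stage 2a subjects.

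**The concern.** The first primary objective is to describe safety, and the protocol calls the trial dose-ranging. A harm that rises with dose would be expected to show most at 4×10^9 PFU, ten times the selected dose. That group has no estimated difference from placebo in the final tables. SAP 6.6 also lets the interim drop doses with safety issues, so a dose dropped for that reason would leave the only primary safety contrast by design. SAP section 15 reports no change to the planned analyses, so the narrowing is not explained.

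Separately, the selected dose's Stage 2a AE data count both in the choice of dose and in the final estimate. No footnote or Stage 2b-only estimate is planned.

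**Working it through.** **Arm sizes.** Protocol 3.1 gives 6 sentinels and 32 Stage 2a subjects at 1:1:1:1, so 8 per arm. Stage 2b adds about 12 to 17 per arm (Protocol Figure 1; 17 is the maximum in 10.2). The total is 6 + 32 + 2×17 = 72, as the protocol states. Final arms are 8 + 12 = 20 to 8 + 17 = 25. Two doses × 8 = 16 Stage 2a subjects fall outside Table 45. The sentinels were assigned, not randomized, and are left out below.

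**Event rate.** The documents give no Grade 2+ rate and no precision target for this endpoint. The rates below are assumptions.

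**Selection effect if safety alone decided.** Take three doses with the same true rate p and 8 subjects each, choose the lowest observed rate, then pool with m new subjects:

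bias = [8/(8+m)] × (expected minimum of three Binomial(8,p)/8 − p)

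| p | Expected minimum | Stage 2a shift (points) | × 8/20 | × 8/25 |
|---|---|---|---|---|
| 0.30 | 0.168 | −13.2 | −5.3 | −4.2 |
| 0.40 | 0.257 | −14.3 | −5.7 | −4.6 |
| 0.50 | 0.352 | −14.8 | −5.9 | −4.7 |

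**Selection effect if only the worst-looking dose is dropped** and one of the other two is taken at random. Simulation (400,000 runs; p from 10% to 50%; 20 and 25 per arm) gives −1.4 to −2.9 points. As a check at p = 0.5, the expected maximum is by symmetry 1 − 0.352 = 0.648. The mean of the other two is (1.5 − 0.648)/2 = 0.426, a shift of −7.4 points, or −3.0 × 8/20-weighted and −2.4 × 8/25-weighted. This agrees with the simulation to within rounding.

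**Precision of the planned contrast.** The half-width is about 1.96 × √(2p(1−p)/n). With p = 0.3 and n = 25 it is 1.96 × √0.0168 = 25 points. With p = 0.5 and n = 20 it is 1.96 × √0.025 = 31 points. The Miettinen–Nurminen method named in Table 45 gives ±24 points at 6/25 in each arm and ±27 at 5/20 in each arm.

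**Precision of an added 8-versus-8 contrast (Miettinen–Nurminen).** At 2/8 in each arm the result is 0 (−43 to +43). At 4/8 versus 2/8 it is +25 (−23 to +64).

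**All phage versus placebo, stratified by stage.** Information per stage is n1·n2/(n1+n2).

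- Selected dose: Stage 2a 8·8/16 = 4; Stage 2b 12·12/24 = 6 or 17·17/34 = 8.5; total 10 or 12.5.
- All phage: Stage 2a 24·8/32 = 6; Stage 2b as above; total 12 or 14.5.
- Standard error ratio: √(10/12) = 0.913 or √(12.5/14.5) = 0.928, so 9% or 7% smaller.

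**The case against.** The strongest reply is that the safety data are all there. A reader might infer that the highest dose goes unreported or appears only in Table 44. The documents do not support that. SAP 9.3.2 adds Stage 2a AE displays by arm, with the concurrent placebo group: Tables 42, 47, 50 and 53 and Figures 15 and 18. Protocol 8.1.1 records AEs only if they are Grade 2 or higher, or Grade 1 and related, so these displays largely cover the primary endpoint's events. What is missing is a difference and its interval, which a reader could work out. This reply stands and lowers the weight of the point.

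A reader might also infer that reuse of selection data pulls the contrast towards no excess harm. That is not established. The addendum gives no weighting of safety against colony counts. Protocol 2.3.1 says bacterial lysis may itself cause flushing, haemodynamic changes and respiratory difficulty, so choosing on colony-count reduction could raise the AE rate. Protocol 8.7.2 has the advisory group weigh AEs and log reductions through Day 8, whereas SAP 6.2 times the interim after Day 30 follow-up. The link between the selection data and the Day 30 endpoint is therefore also uncertain.

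The conflict with the protocol is one of breadth. Protocol 10.5.5 and its Table 3 do not require a difference for each dose, and two doses were always to be dropped. Finally, the interim tables sit in an advisory group charter that is not among these documents. A highest-dose contrast may exist there, so the point is confined to the final-analysis shells.

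The argument that wide intervals make extra rows pointless carries less weight. The study plans no formal testing, so a descriptive estimate costs no alpha, and its width shows how little 8 subjects per arm can exclude.

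**Conclusion.** The point holds, at minor severity. Table 45 is narrower than Protocol 10.5.1 and the safety grouping in SAP 6.1, and two of the three doses have no estimated difference from placebo on the primary safety endpoint in the final tables.

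The effect of selection on the one contrast shown is about 4–6 points too low under safety-only selection among equally safe doses at assumed rates of 30%–50%. It is about 1.4–2.9 points if only the worst-looking dose was dropped (rates 10%–50%). Both figures assume that selection on colony counts is neutral for AEs. The documents do not settle that, so the actual size and direction are unknown. Either figure is small beside a half-width of about 25–31 points.

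**What to change.** Keep the selected-dose contrast. In Table 45, for the Any SOC row only, add descriptive estimates with 95% intervals:

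- each of the three doses versus the concurrent Stage 2a placebo group;
- all phage doses versus placebo, stratified by Stage 2a and 2b. Stratification is needed because the phage-to-placebo ratio is 3:1 in Stage 2a and 1:1 in Stage 2b. This row averages over a 100-fold dose range and could dilute a harm that rises with dose, so it does not replace the per-dose rows.

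Add a footnote that the selected-dose contrast includes subjects whose data were used to choose the dose, and bring the wording of SAP 8.1.1 into line.

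The cost is four rows, one footnote and a sentence in the SAP, with no new data. The downside is the wide 8-versus-8 intervals, which should be labelled descriptive.

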**Table 55: Summary of Fatal On-Therapy SAEs by MedDRA Preferred Term, and Treatment Group – Safety Population**

[Implementation note: Sort this table by decreasing frequency for ‘All Subjects’.]

Preferred Term	4x10  PFU Dose (N=X)			4x10  PFU Dose (N=X)			4x10  PFU Dose (N=X)			Placebo (N=X)			All Subjects (N=X)		
	n	%	Events	n	%	Events	n	%	Events	n	%	Events	n	%	Events
Stage 1															
All	x	x	x	x	x	x	x	x	x	x	x	x	x	x	x
PT1	x	x	x	x	x	x	x	x	x	x	x	x	x	x	x
PT2	x	x	x	x	x	x	x	x	x	x	x	x	x	x	x
Etc															
Stage 2a															
...															
Stage 2a and 2b															
...															

Note: N=Number of subjects in the Safety Population.

### 14.3.2 Listing of Deaths, Other Serious and Significant Adverse Events

**Table 56: Listing of Serious Adverse Events**

Adverse Event	No. of Days Post Associated Dose (Duration)	No. of Days Post Dose the Event Became Serious	Reason Reported as an SAE	Severity	Relationship to Study Treatment	If Not Related, Alternative Etiology	Action Taken with Study Treatment	Subject Discontinued Due to AE	Outcome	MedDRA System Organ Class	MedDRA High Level Term	MedDRA Preferred Term
Subject ID:, Treatment Group:, AE Number:												
Comments:												
Subject ID:, Treatment Group:, AE Number:												
Comments:												

**Table 57: Listing of Adverse Events of Special Interest**

This table will be similar to Table 46.

[Implementation note: Exclude 'No days post dose event became serious', 'Reason reported as an SAE' columns.]

**Table 58: Listing of Adverse Events Leading to Discontinuation**

This table will be similar to Table 46.

[Implementation note: Exclude 'No days post dose event became serious', 'Reason reported as an SAE' and 'Subject discontinued due to AE' columns.]

**Table 59: Listing of Subjects Whose Outcome was Fatal During the Study**

This table will be similar to Table 46.

[Implementation note: Exclude 'No days post dose event became serious', 'Reason reported as an SAE', 'Subject discontinued due to AE', and 'Action taken with study treatment' columns.]

### **14.3.3 Narratives of Deaths, Other Serious and Significant Adverse Events**

(Not included in SAP, but this is a placeholder for the CSR)

#### 14.3.4 Abnormal Laboratory Value Listings (by Subject)

**Table 60: Listing of Abnormal Laboratory Results - Chemistry**

[Implementation Note: This listing is included in the table shells document, as it is included in the body of the CSR. This listing should include all hematology results for any subject that had at least one abnormal chemistry laboratory result. A complete listing of all laboratory results is included in the listings document. In the Laboratory Parameter column, indicate the units after the parameter, e.g., Hemoglobin (g/dL). This listing is not color-coded, but the severity should be included in parentheses after the result, e.g., 16.2 (mild). In the “If Not Related, Alternate Etiology” column, merge the 2 data fields for collecting alternate etiology, separate by a colon. In the CSR, Subject ID should be USUBJID (not PATID) for purposes of de-identification.]

Subject ID	Treatment Group	Sex	Age (years)	Planned Time Point	Actual Study Day	Laboratory Parameter (Units)	Result (Severity)	Relationship to Treatment	If Not Related, Alternate Etiology	Action Taken with Study Treatment	Subject Discontinued Due to Result?

**Table 61: Listing of Abnormal Laboratory Results - Hematology**

[Implementation Note: This listing is included in the table shells document, as it is included in the body of the CSR. This listing should include all hematology results for any subject that had at least one abnormal hematology laboratory result. A complete listing of all laboratory results is included in the listings document. In the Laboratory Parameter column, indicate the units after the parameter, e.g., Hemoglobin (g/dL). This listing is not color-coded, but the severity should be included in parentheses after the result, e.g., 16.2 (mild). In the “If Not Related, Alternate Etiology” column, merge the 2 data fields for collecting alternate etiology, separate by a colon. In the CSR, Subject ID should be USUBJID (not PATID) for purposes of de-identification.]

Subject ID	Treatment Group	Sex	Age (years)	Planned Time Point	Actual Study Day	Laboratory Parameter (Units)	Result (Severity)	Relationship to Treatment	If Not Related, Alternate Etiology	Action Taken with Study Treatment	Subject Discontinued Due to Result?

**Table 62: Listing of Abnormal Laboratory Results – Liver Function Tests**

[Implementation Note: This listing is included in the table shells document, as it is included in the body of the CSR. This listing should include all urinalysis results for any subject that had at least one abnormal urinalysis laboratory result. A complete listing of all laboratory results is included in the listings document. In the Laboratory Parameter column, indicate the units after the parameter, e.g., Hemoglobin (g/dL). This listing is not color-coded, but the severity should be included in parentheses after the result, e.g., 16.2 (mild). In the “If Not Related, Alternate Etiology” column, merge the 2 data fields for collecting alternate etiology, separate by a colon. In the CSR, Subject ID should be USUBJID (not PATID) for purposes of de-identification.]

Subject ID	Treatment Group	Sex	Age (years)	Planned Time Point	Actual Study Day	Laboratory Parameter (Units)	Result (Severity)	Relationship to Treatment	If Not Related, Alternate Etiology	Action Taken with Study Treatment	Subject Discontinued Due to Result?

### 14.3.5 Displays of Laboratory Results

#### 14.3.5.1 Chemistry Results

**Table 63: Chemistry Laboratory Results by Parameter, Maximum Severity, Time Point, and Treatment Group – Any Chemistry Parameter**

[Implementation note: If no missing or outside normal range (ONR) results are reported, these columns will not be included, and corresponding footnotes should be removed. If parameter is not graded then only ‘Within Normal Range’, ‘Outside Normal Range’, and ‘Missing’ columns will be included.]

Treatment group order: All subjects,  $4 \times 10^7$  PFU Dose,  $4 \times 10^8$  PFU Dose,  $4 \times 10^9$  PFU Dose, Placebo.]

Time Point	Treatment Group	N	None		Outside Normal Range a		Mild/ Grade 1		Moderate/ Grade 2		Severe/ Grade 3		Missing	
			n	%	n	%	n	%	n	%	n	%	n	%
Stage 1														
Baseline	All Subjects (N=X)	x	x	xx	x	xx	x	xx	x	xx	x	xx	x	xx
	...													
	Placebo	x	x	xx	x	xx	x	xx	x	xx	x	xx	x	xx
Day 2	All Subjects (N=X)	x	x	xx	x	xx	x	xx	x	xx	x	xx	x	xx
	...													
Day 5	All Subjects (N=X)	x	x	xx	x	xx	x	xx	x	xx	x	xx	x	xx
	...													
Day 8	All Subjects (N=X)	x	x	xx	x	xx	x	xx	x	xx	x	xx	x	xx
	...													
Day 12 b	All Subjects (N=X)	x	x	xx	x	xx	x	xx	x	xx	x	xx	x	xx
	...													
Day 30	All Subjects (N=X)	x	x	xx	x	xx	x	xx	x	xx	x	xx	x	xx
	...													
Max Severity Post Baseline	All Subjects (N=X)	x	x	xx	x	xx	x	xx	x	xx	x	xx	x	xx
	...													

**Table 63: Chemistry Laboratory Results by Parameter, Maximum Severity, Time Point, and Treatment Group – Any Chemistry Parameter (continued)**

Time Point	Treatment Group	N	None		Outside Normal Range a		Mild/ Grade 1		Moderate/ Grade 2		Severe/ Grade 3		Missing	
			n	%	n	%	n	%	n	%	n	%	n	%
Stage 2a														
...														
Stage 2a and 2b														
...														

Notes: The “Max Post Baseline” rows indicate the maximum severity experienced by each subject at any time point post baseline, including unscheduled assessments.

N=Number of subjects in the Safety Population

aPost-dose measurements that were outside the normal range but did not meet the definition for an AE due to the value being less than or equal to the measurement at baseline will be categorized as “Outside Normal Range”

bOnly data from Stage 1 subjects will be summarized for this visit. Any Stage 2a subjects with Day 12 data will be included only in lab listings.

Tables with similar format:

**Table 64: Chemistry Laboratory Results by Parameter, Maximum Severity, Time Point, and Treatment Group – Serum Creatinine**

**Table 65: Chemistry Laboratory Results by Parameter, Maximum Severity, Time Point, and Treatment Group – Blood Urea Nitrogen (BUN)**

